## 4.7 INFORMED CONSENT PROCESS

### 4.7.1 General process

Prior to enrolling in the clinical study and conducting study-specific procedures, all subjects will be consented, as required by applicable regulations and the center's IRB. The consent form must be signed and dated by the subject and by an investigator and the person obtaining the consent if not the investigator.

The principal investigator or his/her authorized designee will conduct the Informed Consent Process. This process will include a verbal discussion with the subject on all aspects of the clinical study that are relevant to the subject's decision to participate in the clinical study.

The subject shall be provided with the informed consent form that is written in a language that is understandable to the subject and has been approved by the center's IRB. Failure to obtain informed consent from a subject prior to study enrollment should be reported to the reviewing center's IRB consistent with the center's IRB reporting requirements.

## 5.0 DRUG UNDER INVESTIGATION

### 5.1 DRUG DESCRIPTION

Amiodarone is a class III antiarrhythmic, which works by a prolongation of the myocardial cell action potential duration and refractory period and noncompetitive  $\alpha$ - and  $\beta$ -adrenergic inhibition.

### 5.2 INTENDED INDICATION

The intended indication is to use the intraoperative application of an amiodarone containing hydrogel in patients undergoing lung transplantation in order to decrease post-operative atrial fibrillation.

### 5.3 AMIODARONE HYDROGEL

The Amiodarone Hydrogel will be prepared per study protocol (see attached). CoSeal Surgical Sealant (Baxter Healthcare) consists of 2 formulations of synthetic polyethylene glycols, a dilute hydrogen chloride solution along with a sodium phosphate/sodium carbonate solution. These separate solutions are mixed at the time of application to form a hydrogel. Amiodarone hydrochloride powder (1mg/kg) will be mixed with CoSeal at the time of application to form an amiodarone containing hydrogel. The dosing of amiodarone is based on previous study using amiodarone hydrogel in post-operative coronary artery bypass patients. This hydrogel will be delivered utilizing a CO2 driver along the pulmonary vein and arterial anastomoses, and to the surface right and left atria.

Table 1. Summary of Proposed Drugs/Drugs

Drug Component	Model/Type	Investigational or Market Released
Amiodarone	Amiodarone	1985 Market Release
CoSeal	CoSeal	2003 Market Release

### 5.4 DRUG ACCOUNTABILITY

The Principal Investigator or an authorized designee will maintain separate drug accountability logs documenting the use of each of the products above. For Amiodarone, only lot/batch/serial number or unique code, dates of dispensation, subject identification, date of use, expiration date, and final disposition of drug will be documented. For the CoSeal, a dedicated study accountability log will document the date of receipt, the identification of each drug (batch number, serial number or unique code), the subject identification, the date of use, the location, the expiration date and final disposition.

### 5.5 DRUG HANDLING AND STORAGE

All products will be stored, according to the labeling. Please refer to the product labeling for additional information on drug handling and storage.

## 6.0 PROCEDURES

A subject is considered to have successfully completed the study upon completion of the 1-year visit

	Screening Visit	Baseline Data Collection	Lung Transplant and hospital follow up	Standard of Care Follow up
Consent Process	X			
Data collection from medical records		X	X	X
Confirm Eligibility	X	X	X	
Application of Amiodarone gel			X	

### 6.1 PROCEDURES

The clinical study will be conducted in accordance with the CIP. All parties participating in the conduct of the clinical study will be qualified by education, training, or experience to perform their tasks and this training will be documented appropriately.

The clinical study will not commence until approval from the IRB and relevant regulatory authorities are obtained.

### 6.2 Visit Schedule

#### 6.2.1 Screening

Study personnel will screen all patients listed on the lung transplant waiting list to determine subject eligibility for the study.

Potential subjects will be contacted to explain the study and determine if they would be interested in participating.

#### 6.2.2 Consent

If potential subjects are interested in participating in the study; they will meet with a study team to discuss the study and sign consent. No study procedures or data collection will occur before a consent form is signed.

#### 6.2.3 Baseline data collection

Data will be collected from the subject's medical records including medical/surgical history, physical exam, current medications, laboratory assessments, electrocardiogram results, pulmonary function test, CT scan results. These tests are conducted as standard of care for subjects undergoing lung transplant.

#### 6.2.4 Prior to lung transplant

When a consented subject is informed that they are scheduled for a lung transplant, the study team will review their medical record to confirm they are still eligible to participate in the study. If they meet any of the exclusion criteria since the initial consent was signed, they will be considered a screen failure and will not undergo the study procedure.

#### 6.2.5 During Lung Transplant Surgery

During the lung transplant surgery the amiodarone-containing hydrogel will be delivered utilizing a CO2 driver along the pulmonary vein and arterial anastomoses, and to the surface of the right and left atria.

### **6.2.6 Follow up data collection**

Data will be collected from the subject's medical records during their standard of care visits post transplant. Standard of care visits include weekly Clinic visits for 1-month post discharge following lung transplantation. Patients will then have monthly regularly scheduled clinic appointments for the first year after transplantation.

In case the subject was already consented to participate in the study, but becomes ineligible by a change in status so that they no longer meet inclusion/exclusion criteria, the following actions will be taken.

- If study procedure/drug implant has not occurred:
- Document enrollment information (name of the study, date of consent and inclusion/exclusion) in the hospital records; complete the Enrollment and Withdrawal Forms. The form must be authorized / approved by the principal or delegated investigator.
- Inform the subject about the screen failure.
- The EC/IRB and CA should be notified appropriately about any deviations with regards to obtaining the informed consent (if applicable).

### **6.3 EARLY TERMINATION**

The study team will attempt to collect all relevant information for the study subjects who withdraw from the study early (including CRF Study Completion Form). The following information will be collected:

- Updated medical and surgical history
- Assessment of AEs that occurred since the last visit
- Abbreviated physical examination (only significant changes since Enrollment) including vital signs (temperature, heart rate, respiratory rate, blood pressure), and weight
- Medication Review

All reasonable efforts will be made to retain subjects in the clinical trial until its completion. Subjects lost to follow-up will be withdrawn only after a minimum of two documented phone calls are made by personnel at the study center to the patient or emergency contact.

### **6.4 CRITERIA AND PROCEDURES FOR SUBJECT WITHDRAWAL OR DISCONTINUATION**

Subjects must be informed about their right to withdraw from the study at any time and for any reason without sanction, penalty or loss of benefits to which the subject is otherwise entitled and withdrawal from the study will not jeopardize their future medical care or relationship with the investigator. Subjects will be asked to specify the reason for the termination, but have the right not to answer.

The investigator may decide to withdraw a subject from the study at any time with reasonable rationale. The subject's future care will not be influenced by a decision, voluntary or otherwise, to withdraw from the study. All reasonable efforts should be made to retain the subject in the clinical study until completion of the study.

Reasons for subject's withdrawal include, but are not limited to:

- Subject refuses to continue participating in the study
- Subject does not meet the inclusion/exclusion criteria and does not require additional follow-up for safety reasons.
- Subject is deceased (cause must be documented)
- Subject's non-compliance
- Subject's participation is terminated by the PI or investigator, although the subject consented, since participation is no longer medically appropriate
- Subject is 'lost to follow up': Subject does not adhere to the scheduled follow up visits but has not explicitly requested to be withdrawn from the clinical study. Site personnel should at all times make

all reasonable efforts to locate and communicate with the subject in order to achieve subject compliance to the scheduled follow up visits:

1. A subject will be considered 'Lost to Follow Up' after a minimum of 2 phone calls of a physician or delegate at the investigational site to the subject or contact. These 2 phone calls need to be documented in the subject's hospital records.

Note: If a subject misses one or more of the scheduled follow up visits (inclusive of the assigned visit windows), this will be considered as a missed visit. The subject may therefore still return for subsequent visits and will not be excluded from the study.

If a subject withdraws from the clinical study, the site will record the subject's reasons for withdrawal (if available), on a Withdrawal CRF.

When subject withdrawal from the clinical study is due to a study related adverse event the subject will be followed until resolution of that adverse event or determination that the subject's condition is stable. The status of the subject's condition should be documented at the time of withdrawal.

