#### Exclusion Criteria

- Patients with previous history of atrial fibrillation
- Patients with previously document allergy or adverse reaction to amiodarone
- Patients with previous ablation for atrial fibrillation
- Patients with an implantable pacemaker
- Patients who are pregnant

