### 4.6.2 Point of Enrollment

Subjects are considered in screening for the study when the subject has provided written Subject Informed Consent. (Refer to section 4.7 for the Informed Consent Process). Subjects are considered enrolled when they have the study intervention.

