## 8.2 ADHERENCE TO THE CLINICAL INVESTIGATION PLAN

A deviation is defined as an event where the clinical investigator, site personnel, sponsor or sponsor representative did not conduct the clinical study according to the Clinical Investigational Plan, IRB requirements or the Investigator Agreement. The investigator is not allowed to deviate from the CIP, except as specified under emergency circumstances.

In some cases, failure to comply with the CIP may be considered failure to protect the rights, safety and well being of subjects, since the non-compliance exposes subjects to unreasonable risks. For example, failure to adhere to the inclusion/exclusion criteria: these criteria are specifically defined by the investigator/manufacturer to exclude subjects for whom the drug is not beneficial and the use involves unreasonable risks. This may be considered failure to protect the rights, safety and well being of the enrolled subject. Similarly, failure to perform safety assessments intended to detect adverse events may be considered failure to protect the rights, safety and well being of the enrolled subject. Investigators should seek minimization of such risks by adhering to the CIP.

Simultaneously, in the event that adhering to the CIP might expose the subject to unreasonable risks, the investigator is also required to protect the rights, safety and well being of the subject by intentionally deviating from the requirements of the CIP, so that subjects are not exposed to unreasonable risks.

It is the responsibility of the investigator to provide adequate medical care to a subject enrolled in a study.

Regulations require that the PI maintain accurate, complete, and current records, including documents showing the date of and reason for every deviation from the Clinical Investigational Plan. Relevant information for each deviation will be documented on a Deviation Case Report Form.

Regulations require Investigators obtain approval from IRB before initiating changes in or deviations from the protocol, except when necessary to protect the life or physical well being of a subject in an emergency. Under emergency circumstances, deviations from the CIP to protect the rights, safety and well being of human subjects may proceed without prior approval of the IRB. Such deviations shall be documented and reported to the IRB as soon as possible, but no later than 5 working days.

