## Post-operative Information

ICU Length of Stay (hour)

\_\_\_\_\_

Atrial Fibrillation at discharge

- Yes
- No

Treatment for A Fib

- None
- Amiodarone IV
- Amiodarone Oral
- Cardioversion (inc chemical CV)
- Rhythm device (pacemaker/ICD) placement
- Other

A Fib resolved at discharge

- Yes
- No

Bradycardia

- None
- Yes - not treated
- Yes - required pacing

Discharge Status

- Alive
- Dead

Discharge Date

\_\_\_\_\_  
(death date if patient died in hospital)

Atrila Fibrillation at 1 week

- Yes
- No

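### The plan does not say what happens to a gel-treated patient found or becoming ineligible after the gel, and sections 6.4 and 14.1 together allow that patient to be withdrawn and replaced

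*Combined protocol and SAP*

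**What the plan says.** **Withdrawal.** Section 6.4 gives as one reason "Subject does not meet the inclusion/exclusion criteria and does not require additional follow-up for safety reasons". The reason is not confined to the time before treatment. The same section adds that "The investigator may decide to withdraw a subject from the study at any time with reasonable rationale", and its list of reasons is open-ended.

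**Enrolment.** Section 4.6.2: "Subjects are considered enrolled when they have the study intervention". An enrolled subject is therefore a treated subject.

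**Loss of eligibility.** Section 6.2.4 requires a record review before transplant; anyone who then meets an exclusion criterion is a screen failure and gets no gel. Section 6.2.6, on follow-up, addresses a consented subject who "becomes ineligible by a change in status so that they no longer meet inclusion/exclusion criteria", but lists actions only for the case where the study procedure has not taken place. The section 6.0 table marks the eligibility check at screening, at baseline and under "Lung Transplant and hospital follow up".

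**Exclusion criteria (4.5).** These include "Patients with previous history of atrial fibrillation", an earlier documented allergy or adverse reaction to amiodarone, and an implantable pacemaker. Only the pacemaker criterion, of these three, carries no word placing it in the past. The post-operative case report form (CRF) page in Appendix E lists "Rhythm device (pacemaker/ICD) placement" among treatments for AF.

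**Analysis.** Section 14.1 specifies an as-treated analysis. Patients who drop out or withdraw ahead of the primary endpoint are excluded and replaced so that at least 20 are enrolled. The primary endpoint (4.4.1) is AF during the initial hospitalization.

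**The concern.** In a single-arm study against historical controls, the treated group should be fixed at treatment. Here a treated patient can later be declared ineligible, withdrawn, and replaced if the withdrawal is judged to precede the endpoint. If the reason for the declaration is linked to AF or its treatment, removal depends on outcome. It can act only on the gel arm, because chart-derived controls cannot be withdrawn or replaced in this way.

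In hospital this would lower the observed gel AF rate. After discharge, withdrawal would lose first-year AF and one-year survival, both secondary endpoints, for the patients concerned. With 20 treated patients, one or two removals are visible in the result.

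**Working it through.** **1. Does the text reach treated patients?** The 6.4 reason has no time limit, and its condition about safety follow-up has most meaning for someone who has received the gel. Section 6.2.6 has a branch for before the procedure and none for after. Because enrolment occurs at the gel, the replacement rule in 14.1 bears on treated patients; an untreated screen failure never counted towards the 20. So withdrawal of a treated patient on this ground is permitted, though nowhere required.

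**2. Which criteria could link removal to outcome?**
- *Earlier AF found late.* An episode that truly predates surgery meets the AF criterion even on a baseline reading. Eligibility rests on medical records (6.2.3, 6.2.4). If new AF prompts a closer history (an assumption), discovery is more likely in patients who have the endpoint.
- *Pacemaker placed after the gel.* The criterion has no baseline qualifier, and the CRF foresees device placement as a treatment for post-operative AF. Against this, the pre-operative CRF page has its own field for an earlier pacemaker, which suggests that baseline status was meant.

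**3. Size (illustration only).** The plan gives no withdrawal rate, significance level or sidedness, so it has no figure to reproduce.
- From the documents: AF rate p = 0.30 (14.1), 20 gel patients (4.2.3, 14.1), 50 controls (4.2.3), exact or chi-square test (14.1).
- Assumed: two-sided 5% level; no true gel effect; a share q of gel AF cases removed and replaced; withdrawal before discharge counted as before the endpoint.

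Expected gel AF rate after removal and replacement = p(1 − q)/(1 − pq). Patients treated to keep 20 = 20/(1 − pq). AF cases removed = treated × pq.
- q = 0.10: 0.27/0.97 = 27.8%; 20.6 treated; 0.6 removed
- q = 0.20: 0.24/0.94 = 25.5%; 21.3 treated; 1.3 removed
- q = 0.30: 0.21/0.91 = 23.1%; 22.0 treated; 2.0 removed

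The chance of a false result favouring gel is the sum, over all tables from Binomial(20, observed rate) and Binomial(50, 0.30), of the probabilities of tables with p ≤ 0.05 and the lower rate on gel:

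| q | Gel AF | Fisher | Chi-square (uncorrected) |
|---|---|---|---|
| 0 | 30.0% | 1.5% | 2.3% |
| 0.10 | 27.8% | 2.2% | 3.4% |
| 0.20 | 25.5% | 3.3% | 5.0% |
| 0.30 | 23.1% | 5.1% | 7.5% |

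**4. Sensitivity to single patients.** Against 15/50 controls, Fisher p is 1.00 for 6/20, 0.55 for 4/20, 0.24 for 3/20 and 0.028 for 1/20. Two AF cases replaced by AF-free patients would not make 6/20 significant, but would turn 3/20 into a significant 1/20.

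**The case against.** The strongest reply is that the plan intends eligibility to be settled at baseline. Much of it stands.

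- A reader might infer that post-operative AF, or a reaction to the gel, itself makes a treated patient ineligible. The documents do not support that. Both criteria are worded as prior conditions, post-operative AF is the endpoint, and the CRF records earlier arrhythmia and earlier pacemaker on its pre-operative page, apart from post-operative events.
- A reader might take the 6.0 table as showing eligibility checks on the ward. The column also contains the gel application, so the mark fits the pre-transplant check in 6.2.4. The standard-of-care follow-up column has no eligibility mark; removal after discharge rests on 6.4 alone.
- A reader might see a contradiction with 8.2, which gives "failure to adhere to the inclusion/exclusion criteria" as an example of non-compliance. There is none: a deviation can be recorded and the subject also withdrawn. Section 8.2 simply does not say whether the patient stays in.
- The safety condition in 6.4 narrows the route, since a patient with a new device or a drug reaction would often need follow-up. Sections 6.3, 6.4 and 9.3 also ask for retention and for monitoring of related events. These limit the route without closing it.
- A patient with AF has arguably already reached the primary endpoint, so 14.1 might not replace that patient. The phrase is undefined; on this reading the in-hospital effect on the primary endpoint largely disappears.

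The study is also a pilot not sized on power, so a false significant result matters less than in a confirmatory trial. The estimated AF rate is still meant to inform a larger randomized trial (4.2).

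**Conclusion.** The concern holds as a gap in the rules: 6.4 sets no time limit, 6.2.6 has no post-gel branch, and 14.1 excludes and replaces on an undefined phrase. Together they permit, but do not prescribe, outcome-related removal from the gel arm alone, by the two routes in the working. The pacemaker route is the less certain of the two.

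The likely effect is modest. With 6 AF cases expected among 20 (0.30 × 20), q from 10% to 30% is about one or two patients, a fall of 2 to 7 percentage points in expected gel AF and a Fisher false-positive chance that stays near or below 5%. These figures depend on the assumed q and on counting withdrawal before discharge as before the endpoint. The post-discharge loss of secondary endpoints does not depend on that phrase. Because the correction is cheap, it should be made.

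**What to change.** 1. In 6.2.4, 6.2.6 and 6.4, state that eligibility is judged for the last time before the gel is applied.
2. In 6.4, limit the ineligibility reason to subjects not yet treated.
3. In 6.2.6, add the missing branch: ineligibility found or arising after the gel is documented, and if found later it is recorded as a deviation.
4. In 14.1, state that a gel-treated subject is not excluded or replaced for ineligibility found or arising after the gel, and stays in follow-up and every analysis as far as consent allows. Without this step, changing 6.4 alone leaves the analysis rule open.
5. Optionally, add one sensitivity analysis excluding subjects whose ineligibility was documented before transplant, with the same chart search applied to the controls.

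The cost is protocol wording, plus the control chart search if item 5 is adopted. The downside is that a few treated patients who were strictly ineligible remain in the main analysis. The investigator's general discretion to withdraw subjects is wider than this point and is not removed by these changes.

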## **7.0 RISK**

There are numerous risks when undergoing lung transplantation. Subjects will be informed of these risks and sign a separate surgery consent. Currently the only identified potential risk incurred by participating in this study is temporary bradycardia (slow heart rate). In a previous study in patients undergoing coronary artery bypass surgery, a similar intervention using amiodarone gel was assessed and the only complication noted in those patients was temporary, not clinically significant bradycardia. In the previous study this was a common complication (greater than 10%), however it was not serious and did not require any additional treatment.

If bradycardia is severe enough to be symptomatic, transvenous pacing may be required, in order to maintain a normal heart rate. The risks from this procedure include but are not limited to: death, femoral hematoma, arrhythmias, fever, cardiac tamponade, deep venous thrombosis, and sepsis.

Animal studies and a previous human study did not demonstrate any evidence that the local application of an amiodarone gel to the heart could result in tissue damage. However, tissue damage has been reported if amiodarone leaks from the vein when using intravenous amiodarone.

A one-time dose of amiodarone will be used in the preparation of the amiodarone hydrogel. While, the dose used in this study is extremely low, there are several known side effects of amiodarone use, which typically occur when amiodarone is administered systemically for an extended period of time. These potential side effects include: nausea, vomiting, photosensitivity, fatigue, dizziness, paraesthesias, constipation, anorexia, visual disturbances, liver damage, pulmonary fibrosis, hypo or hyperthyroidism, insomnia, headache, sleep disturbances, congestive heart failure, cardiac arrhythmias, SA node dysfunction, abdominal pain, hepatic disorders, flushing, abnormal taste and smell, edema, abnormal salivation and coagulation abnormalities.

Any serious, related, and unanticipated adverse events will be reported to the IRB within 5 working days of awareness of the event. All drug related, serious, unanticipated adverse drug reactions will be reported to the company and FDA within 15 working days of the event.

